5.1.2 Premedication

No premedication will be required.

5.1.3 Patient monitoring

The patients will be monitored according to standard clinical routines. Renal function in terms of creatinine is analyzed at baseline and hepatic function will be measured at baseline and after 3, 12 and 24 months. In case of renal or hepatic dysfunction above the described limits measured in blood samples during monitoring period, extended monitoring will be initiated. See 5.1.4 for further information.

Adherence to STUDY MEDICATION is monitored and is registered in the MASTER folder in the DBCG CRF database.

5.1.4 Early stopping rules

- Raising levels of hepatic transaminases to three times the upper limit of normal will require discontinuation of STUDY MEDICATION therapy until normalized hepatic function has returned. Upon normalization, the STUDY MEDICATION can be re-induced.
- Intolerable adverse events deemed related to STUDY MEDICATION (answered "Probable" or "Certain" in CRF), will require discontinuation of STUDY MEDICATION. Upon normalization, the STUDY MEDICATION can be re-induced.
- Myopathy (muscle aching or muscle weakness in conjunction with increase in creatinine phosphokinase values greater than five times the upper limit of normal) will require permanent discontinuation of STUDY MEDICATION.
- Reduced performance status (ECOG>2) will require permanent discontinuation of STUDY MEDICATION.

In case of early stopping of STUDY MEDICATION, all other procedures will continue apart from STUDY MEDICATION. It should be registered in the CRF folder "Master End of Trial" if the patient stops medication (End of treatment) and if the patients for any reasons stops participating in this study (End of trial).

5.1.5 Duration of therapy

All patients will receive atorvastatin or placebo for two years with the exception mentioned in section 5.1.4 or in case of discontinuation requested by the patient. Atorvastatin is a well-documented drug prescribed for continuous use over several years and intercurrent illness would not indicate discontinuation of atorvastatin, unless symptoms are related to those mentioned in section 5.1.4.

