- Reduced performance status (ECOG>2) will require permanent discontinuation of STUDY MEDICATION.

DURATION OF THERAPY

All patients will receive STUDY MEDICATION (atorvastatin or placebo) for two years.

STUDY MEDICATION will be discontinued if:

- 1. There are any SAFETY concerns.
- 2. Cholesterol-lowering therapy becomes clinically indicated.
- 3. Discontinuation is requested by the participant and/or her treating physician.
- 4. In case of an incident breast cancer event (any invasive breast cancer, including local/regional, contralateral or distant recurrence).

Atorvastatin is a well-documented drug prescribed for continuous use over several years and the appearance of other illnesses would not indicate discontinuation of atorvastatin.

CONCOMITANT THERAPY

During STUDY MEDICATION concomitant drugs are permitted. Caution should be taken in case of:

- Digoxin treated patients should be monitored as coadministration of atorvastatin and digoxin has been shown to increase steady-state plasma digoxin concentrations by approximately 20%. Among digoxin-treated patients, plasma digoxin will be measured at baseline, after 1 week and after 1 month on STUDY MEDICATION and an increase of ≥ 20% at consequently will lead to a reduction in dosage of digoxin.
- 2. Daily intake of grapefruit juice should be avoided during atorvastatin therapy due to the grape fruit induced inhibition of CYP450 system by which atorvastatin is metabolized.
- 3. CYP3A4 inhibitors such as macrolide antibiotics (erythromycin), immunosuppressants (cyclosporine), azole antifungal agents (*i.e.*, itraconazole, ketoconazole), and some antidepressants (*i.e.*, nefazodone) should if possible be avoided during atorvastatin therapy as they may have a potential of increasing plasma concentrations of atorvastatin.

PROCEDURES (Summary)

During STUDY MEDICATION, patients will be assessed for safety and efficacy (see Schedule of Assessments tables).

Patients will receive STUDY MEDICATION for a total of two years (104 weeks).

ASSESSMENTS

EFFICACY

IDFS, defined as the time from randomization until the date of the first occurrence of one of the following events:

- Ipsilateral invasive breast tumor recurrence: invasive breast cancer involving the same breast parenchyma as the original primary.
- Regional invasive breast cancer recurrence: Invasive breast cancer in the axilla, regional lymph nodes, chest wall, and skin of the ipsilateral breast.

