3.2 Exclusion criteria

- History of any prior (ipsi- and/or contralateral) invasive breast carcinoma
- Prevalent cholesterol lowering therapy (statins, fibrates, ezetimibe, PCSK9 inhibitors). These
 patients can be enrolled in the observational cohort given fulfillment of other in- and exclusion
 criteria.
- Evidence of hepatic dysfunction (alanine aminotransferase level more than three times the upper limit of the normal range) or renal dysfunction (creatinine level more than three times the upper limit of the normal range).
- Predisposing factors for rhabdomyolysis, including hypothyroidism, reduced renal function, any muscle – or liver disease, or excessive alcohol consumption above 14 drinks/week AND creatine kinase (CK) measured to more than five times the upper limit (CK only measured in case of predisposing factors).

- ♦ Current medication with potent CYP3A4-inhibitors (e.g. ketokonazole, erythromycin) or gemfibrozile, ciclosporin or danazol.
- Pregnancy or breast-feeding (contraception according to clinical routines for premenopausal, fertile breast cancer patients, that includes non-hormonal contraception such as condom, vaginal diaphragm, or intrauterine device).
- Psychological, familial, sociological or geographical condition potentially hampering compliance with the study protocol and follow-up schedule; these conditions will be discussed with the patient before registration in the trial.
- History of allergic reactions attributed to compounds of similar chemical or biological composition to atorvastatin.

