6.4 After the end of treatment (follow-up)

The follow-up includes assessment of clinical events (recurrences) and overall survival at a yearly basis up to 10 years after inclusion in the study. Patients are followed in the clinic according to the time points for clinical routine visits (up to 10 years depending on menopausal status). Clinical events are recorded at a yearly basis into the DBCG CRF database.

To ensure detection of potential long-term effects and side effects of STUDY TREATMENT, linkage to medical records and the national cancer - and death registries up to 20 years after diagnosis will facilitate long-term follow-up and detection of late recurrences and other secondary cancers. Other possible late side effects will be identified through linkage to the Hospitalization Registry.

Importantly, patient reported outcomes are to be reported yearly through a RedCap-based model up to 10 years after study inclusion.

6.5 Summary table 1

Study procedures for the randomized cohort described in the following table:

Required Investigations	Baseline (T1)	3 months (+/- 14 days) (T2)	6 months (+/- 14 days) (T3)	1 year (+/- 14 days) (T4)	2 years (+/- 14 days) (T5)	Yearly, (+/- 28 days) 3-10 years (T6)
Inclusion - exclusion criteria (DBCG)	X					
Informed consent	X					
Randomization (DBCG)	X					
CRF Master flow (DBCG)	X	X ³	x ³⁴	X ³⁴	X ³⁴	X ⁴
CRF Master AE (DBCG)	X	X ³⁴	X ³	X ³⁴	X ³	
STUDY MEDICATION START/ADHERENCE (DBCG)	X	Х	Х	Х	Х	
Patient Reported Outcome (RedCap)	X	X	X	X	X	X
Pathological response (Only patients in neo- adjuvant cohort)			Х			
HCG⁵(serum or urine)	X					
Hepatic (ALT) function	X ²	Х		Х	Х	
Renal (creatinine) function	X ²					
Creatine kinase ¹	(X)					
Translational blood samples	X		(X neoadjuvant cohort patients)	X	X	
Translational tumor tissue samples from existing tissue	X		(X neoadjuvant cohort patients)			

^{1.} Predisposing factors for rhabdomyolysis, including hypothyroidism, reduced renal function, any muscle – or liver disease, or excessive alcohol consumption above 14 drinks/week AND creatine kinase (CK) measured to more than five times the upper limit (CK only measured in case of predisposing factors).

- 2. Blood samples are allowed to be taken up to 28 days before T1
- 3. Either done by phone interview or attendance at the clinic
- 4. Data collected from the patient file
- 5. Only fertile women

6.6 Summary table 2

Study procedures for the observational cohort are described in the following table:

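### The synopsis and section 5.1.5 give conflicting lists of reasons to stop study medication, and neither list names pregnancy or breast-feeding although both bar entry

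*Protocol*

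**What the plan says.** **Duration in the body.** Section 5.1.5: "All patients will receive atorvastatin or placebo for two years with the exception mentioned in section 5.1.4". The one further exception is a wish to stop expressed by the woman herself. The section adds that intercurrent illness is no reason to stop unless the symptoms relate to those in 5.1.4.

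**Rules in 5.1.4.** There are four: raised transaminases, intolerable adverse events judged related to study medication, myopathy with raised creatine phosphokinase, and performance status ("Reduced performance status (ECOG>2) will require permanent discontinuation of STUDY MEDICATION").

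**Duration in the synopsis.** Study medication is discontinued for any of four reasons. The first reads "There are any SAFETY concerns" and the third reads "Discontinuation is requested by the participant and/or her treating physician". The other two are that cholesterol-lowering therapy becomes clinically indicated, and that an invasive breast cancer event occurs.

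**Pregnancy.** Section 3.2 and the synopsis exclude "Pregnancy or breast-feeding (contraception according to clinical routines for premenopausal, fertile breast cancer patients", with non-hormonal methods given as examples. Summary table 1 (section 6.5) marks HCG at baseline only, with the footnote "Only fertile women". Section 2.3 plans separate exploratory analyses in pre- and postmenopausal patients. In section 14, congenital malformation appears as a seriousness criterion; no procedure for reporting a pregnancy is given.

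**The concern.** Section 5.1.5 is worded as a closed rule: everyone takes two years of drug except for the listed reasons. The synopsis closes its list differently. In a multicentre, blinded trial of 3,360 women, sites that rely on different parts of the same protocol can treat the same event differently and each be compliant with what they read.

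Pregnancy is where this bears most directly on patient safety. The protocol treats it as incompatible with starting study medication, then gives two years of dosing to a population that includes fertile women without naming it again. Whether a site has a protocol basis to act depends on which section it opens. Overall safety is a secondary endpoint, but nothing in the reporting rules ensures that an exposed pregnancy and its outcome are recorded and can be tabulated by arm.

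**Working it through.** The point depends on no sample size, event count or rate, so the check is a comparison of texts.

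**Step 1: set the two lists side by side.**

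| Reason to stop | Synopsis, Duration of therapy | Sections 5.1.4 and 5.1.5 |
|---|---|---|
| Any safety concern | Yes | Only the four named rules of 5.1.4 |
| Cholesterol-lowering therapy indicated | Yes | Not listed |
| Participant's request | Yes | Yes |
| Treating physician's request | Yes | Not listed |
| Incident invasive breast cancer event | Yes | Not listed |
| Pregnancy or breast-feeding | Not named | Not named |

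The participant's request is the only reason that passes intact from the synopsis to the body. The general safety reason is narrowed to four specific rules, the physician's request is lost, and two further reasons are absent.

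**Step 2: ask whether the difference is only one of brevity.** A shorter list would be harmless if it were open-ended. Section 5.1.5 is not: it gives the drug to all patients and then names its exceptions. The sentence on intercurrent illness points back to 5.1.4 as the controlling list. So the body excludes reasons that the synopsis requires, which is a contradiction and not an abbreviation.

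**Step 3: ask whether the differing reasons can arise.** Indicated lipid-lowering therapy is not remote. Section 1.2 reports, from an adjuvant trial, that such drugs were needed in 25% of patients on letrozole and 16% on tamoxifen. No time frame is given, so these are not two-year rates for this trial, but they show that the mismatch concerns a foreseeable event.

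**Step 4: follow pregnancy through the document.**
- Entry: excluded, in the synopsis and in 3.2.
- Population: fertile women are expected, from the contraception wording in 3.2, the menopausal subgroups in 2.3 and the HCG footnote.
- Testing: HCG is marked at one of the six time points (T1). It is not marked at T2 to T5, the four visits that span treatment.
- Stopping: 0 of 4 rules in 5.1.4 and 0 of 4 reasons in the synopsis name it. Two synopsis reasons (any safety concern, physician's request) are broad enough to cover it; 5.1.5 carries neither.
- Recording: section 14 defines an adverse event as an untoward occurrence, which a pregnancy need not be. It becomes reportable as serious only if it meets a criterion such as congenital malformation or another medically important condition.

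**Step 5: separate the conflict from the gap.** Synopsis against 5.1.4 and 5.1.5 is a conflict between two statements. Section 3.2 against 5.1.5 is a gap: an entry bar with no named counterpart on treatment. Eligibility and continuation are different questions, and 5.1.5 nowhere says that a pregnant woman must continue.

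**The case against.** A reader might infer that a woman who becomes pregnant stays on blinded study drug under the protocol as written. The document does not support that. The synopsis belongs to the same protocol and stops the drug for any safety concern and at the treating physician's request. A condition that bars entry is readily seen as a safety concern. Even under 5.1.5 the woman can ask to stop. This objection stands, and the point is confined accordingly.

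The contraception wording in 3.2 also looks forward into treatment, and patients are monitored under clinical routine. That lowers the chance of the event but does not say what happens if it occurs.

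On recording, 5.1.4 requires any stop of medication to be registered in the end-of-trial CRF folder, and serious related events are reportable. So it would be wrong to say that the data would hold no trace. It is right to say that no dedicated record of the pregnancy and its outcome is required.

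A reader might also want a count of exposed pregnancies. The protocol gives neither the share of fertile women nor a pregnancy rate, so any count would rest wholly on assumed inputs. None is offered in support of severity.

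The objection leaves the difference between the two lists untouched.

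**Conclusion.** The discontinuation text is wrong as written and should be corrected. Section 5.1.5 states a closed rule that conflicts with the wider synopsis list on the general safety reason, the physician's request, indicated cholesterol-lowering therapy and breast cancer events. Pregnancy and breast-feeding arising on treatment are reached only through general synopsis wording that 5.1.5 does not carry, and they have no dedicated record.

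The size is best stated as scope: the conflicting rules apply to all 3,360 planned participants over two years of treatment, and the pregnancy gap applies to the fertile women among them, whose number the protocol does not give. The conclusion rests on reading 5.1.5 as exhaustive, which is its plain sense. It is a fault in the operating text and in safety recording. The sample size and the intention-to-treat comparison of IDFS are not called into question by it.

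**What to change.** 1. Reconcile the synopsis (Duration of therapy) with sections 5.1.4 and 5.1.5 so that the protocol contains one discontinuation list, stated once and cross-referenced. Include the synopsis block on dose adjustments and early stopping in the same pass, because its laboratory triggers also differ from 5.1.4: a creatine kinase trigger at three times the upper limit appears only in the synopsis.
2. Have that list address pregnancy and breast-feeding arising during treatment, in agreement with section 3.2 and the HCG row of Summary table 1. What the site should do, and whether HCG is repeated, is for the sponsor's clinicians to decide; the passages need only agree with that decision.
3. Add a field to the existing Master AE form for each pregnancy during treatment and its outcome, with a matching sentence in section 14, so that these can be reported by arm under overall safety.

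The cost is a text amendment and one CRF field. There is no effect on sample size, randomization or the primary analysis.

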5.1.6 Concomitant therapy

Concomitant drugs during atorvastatin therapy are permitted.

Caution should be taken in case of:

- Digoxin treated patients should be monitored as co-administration of atorvastatin and digoxin has been shown to increase steady-state plasma digoxin concentrations by approximately 20%. Among digoxin-treated patients, plasma digoxin will be measured at baseline, after 1 week and after 1 month on STUDY MEDICATION and an increase of \geq 20% at consequently will lead to a reduction in dosage of digoxin. For patients on digoxin, a note to the physician prescribing digoxin should be sent indicating that the patient participates in a randomized trial with either atorvastatin 80 mg or placebo.
- Daily intake of grapefruit juice should be avoided during atorvastatin therapy due to inhibition of the CYP450 system by which atorvastatin is metabolized.
- CYP3A4 inhibitors such as macrolide antibiotics (erythromycin), immunosuppressants (cyclosporine), azole antifungal agents (i.e. itraconazole, ketoconazole), and some antidepressants (i.e. nefazodone) should if possible be avoided during atorvastatin therapy as they may have a potential of increasing plasma concentrations of atorvastatin.

6 CLINICAL EVALUATION, LABORATORY TESTS, FOLLOW-UP

6.1 Before treatment start

Before treatment start the patient's eligibility should be evaluated which will include:

- Social and psychological conditions according to section 3.
- Medical history and clinical examination.
- Blood samples (hepatic (ALT) and renal (creatinine) parameters, (creatine phosphokinase if predisposing factors, including hypothyroidism, reduced renal function, any muscle – or liver disease, and excessive alcohol consumption)).

Case Report Forms (CRF) in the MASTER folder in the DBCG system will be filled in at baseline.

6.2 Observational cohort

Patients that are not able to participate in the randomized placebo-controlled part of the trial due to prevalent cholesterol lowering therapy (statins, fibrates, ezetimibe, PCSK9 inhibitors), but otherwise fulfil in- and exclusion criteria can be included in the observational cohort. Patients can participate in the observational cohort regardless of the dose of cholesterol lowering therapy. In this cohort no randomization or medical intervention is relevant, otherwise these patients will with a few exceptions follow the study schedule in accordance with the randomized patients.

Adverse events will be registered in the Master folder in the DBCG CRF according to the schedule above. However, SAEs are not to be reported for patients in the observational cohort.

In case the patient terminates cholesterol-lowering medication for any reason, the patient is still followed according to the trial protocol. It should be registered in the CRF folder "Master End of Trial" if the patient stops medication (End of treatment) and if the patients for any reasons stops participating in this study (End of trial).

6.3 During treatment

Adverse events will be registered in the MASTER folder in the DBCG CRF. Herein, protocol compliance will also be assessed and reported.

In addition, patients are instructed to report information addressing patient reported outcome including compliance to STUDY MEDICATION into a REDCap research database at the time points specified below.

Blood samples assessing renal function at baseline and hepatic function at baseline and at the 3, 12, and 24-month visits are collected. Further therapeutic decisions are based on section 5.1.4.

6.4 After the end of treatment (follow-up)

The follow-up includes assessment of clinical events (recurrences) and overall survival at a yearly basis up to 10 years after inclusion in the study. Patients are followed in the clinic according to the time points for clinical routine visits (up to 10 years depending on menopausal status). Clinical events are recorded at a yearly basis into the DBCG CRF database.

To ensure detection of potential long-term effects and side effects of STUDY TREATMENT, linkage to medical records and the national cancer - and death registries up to 20 years after diagnosis will facilitate long-term follow-up and detection of late recurrences and other secondary cancers. Other possible late side effects will be identified through linkage to the Hospitalization Registry.

Importantly, patient reported outcomes are to be reported yearly through a RedCap-based model up to 10 years after study inclusion.

6.5 Summary table 1

Study procedures for the randomized cohort described in the following table:

Required Investigations	Baseline (T1)	3 months (+/- 14 days) (T2)	6 months (+/- 14 days) (T3)	1 year (+/- 14 days) (T4)	2 years (+/- 14 days) (T5)	Yearly, (+/- 28 days) 3-10 years (T6)
Inclusion - exclusion criteria (DBCG)	X					
Informed consent	X					
Randomization (DBCG)	X					
CRF Master flow (DBCG)	X	X ³	x ³⁴	X ³⁴	X ³⁴	X ⁴
CRF Master AE (DBCG)	X	X ³⁴	X ³	X ³⁴	X ³	
STUDY MEDICATION START/ADHERENCE (DBCG)	X	Х	Х	Х	Х	
Patient Reported Outcome (RedCap)	X	X	X	X	X	X
Pathological response (Only patients in neo- adjuvant cohort)			Х			
HCG⁵(serum or urine)	X					
Hepatic (ALT) function	X ²	Х		Х	Х	
Renal (creatinine) function	X ²					
Creatine kinase ¹	(X)					
Translational blood samples	X		(X neoadjuvant cohort patients)	X	X	
Translational tumor tissue samples from existing tissue	X		(X neoadjuvant cohort patients)			

^{1.} Predisposing factors for rhabdomyolysis, including hypothyroidism, reduced renal function, any muscle – or liver disease, or excessive alcohol consumption above 14 drinks/week AND creatine kinase (CK) measured to more than five times the upper limit (CK only measured in case of predisposing factors).

- 2. Blood samples are allowed to be taken up to 28 days before T1
- 3. Either done by phone interview or attendance at the clinic
- 4. Data collected from the patient file
- 5. Only fertile women

6.6 Summary table 2

Study procedures for the observational cohort are described in the following table:

Required	Baseline	3 months	6 months	1 year	2 years	3-10 years
Investigations	(T1)	(+/- 14 days) (T2)	(+/- 14 days) (T3)	(+/- 14 days) (T4)	(+/- 14 days) (T5)	(+/- 28 days) (T6)
Inclusion- exclusion criteria (DBCG)	X					
Informed consent	X					
Registration (DBCG)	X					
CRF Master Flow (DBCG)	X	X ²	X ²	X ²	X ²	X ³
CRF Master AE (DBCG)	X	X ²	X ²	X ²	X ²	
Patient reported outcome (REDCap)	X	X	X	Х	Х	X
Hepatic function (ALT)	X¹					
Renal function (creatinine)	X¹					
Translational blood samples	X			X	Х	
Translational tumor tissue samples from existing tissue	х					

- 1. Blood samples are allowed to be taken up to 28 days before T1
- 2. Either done by phone interview or attendance at the clinic
- 3. Data collected from the patient file

